2.1.2 Primary Safety Endpoint

The primary safety endpoint is a composite endpoint consisting of any one or more of the following events if they are adjudicated by the CEC to be serious adverse events (SAEs) and related to device/procedures as follows:

1. The AtriCure Bipolar System and/or the AtriClip Pro LAA Exclusion System, within 30 days following the epicardial surgical ablation procedure; or
2. The epicardial surgical ablation procedure within 30 days following the epicardial procedure; or
3. The endocardial index procedure (or a repeat endocardial ablation procedure performed during the blanking period) within 7 days following an endocardial ablation procedure.

Events except as otherwise specified for a particular condition include:

- a. death (regardless of cause)
- b. stroke
- c. transient ischemic attack (TIA)

Statistical Analysis Plan		Page 7 of 22
Sponsor	Study	Version
AtriCure	DEEP Pivotal Study	Version 2.0

- d. myocardial infarction (MI)
- e. pulmonary or systemic embolism
- f. pericarditis resulting in an effusion that leads to hemodynamic compromise or requires pericardiocentesis, prolongs hospitalization by more than 48 hours, requires a new hospitalization, or persists for more than 30 days following the ablation procedure
- g. excessive bleeding, defined as one or more of the following:
 - i. re-operation to control bleeding within 7 days post-epicardial surgical procedure; or surgery to control bleeding within 7 days post-endocardial ablation procedure, if related to the device or procedure;
 - ii. receipt of ≥ 2 units of blood transfused in a 24-hour period during the first 7 days post-epicardial surgical procedure, or within the first 7 days post-endocardial ablation procedure, if related to the device or procedure;
 - iii. conversion to sternotomy or thoracotomy that requires ≥ 2 units blood to be transfused, or performed to treat hypotension, cardiac arrest, or repair of a cardiac injury.
- h. wound infection at surgical site requiring re-operation for wound debridement
- i. atrio-esophageal fistula (from the time of surgical procedure through 12-month follow-up visit)
- j. permanent phrenic nerve paralysis, defined as paralysis that remains unresolved at the 12-month follow-up visit
- k. permanent pacemaker implantation that is a direct result of injury to the specialized conduction system (SA node or AV node) during the epicardial surgical ablation procedure.
- l. pulmonary vein (PV) stenosis of $>70\%$, as measured at any time after the endocardial catheter ablation procedure through the 12-month follow-up period
- m. major vascular access complications, including the development of a hematoma, an arteriovenous fistula, or a pseudoaneurysm requiring intervention such as surgical repair or transfusion, prolongs the hospital stay, or requires a new hospital admission

Statistical Analysis Plan		Page 8 of 22
Sponsor	Study	Version
AtriCure	DEEP Pivotal Study	Version 2.0

2.1.3 Secondary Efficacy Endpoints

1. Exclusion of the LAA, defined as lack of fluid communication (<3 mm residual communication with LAA and < 10mm residual pocket) between the LA and LAA. This endpoint will be measured at the 12-month Visit (Visit 11). The AtriClip® effectiveness population will be utilized for this analysis endpoint.
2. Exclusion of the LAA, defined as lack of fluid communication (<3 mm residual communication with LAA and <10 mm residual pocket) between the LA and LAA. The endpoint will be measured at the intra-procedurally (Visit 2), at the Endocardial EP Ablation Procedure (Visit 5). The AtriClip effectiveness population will be utilized for this analysis endpoint.
3. Acute procedural success of epicardial surgical procedure, defined as the percentage of subjects with successful electrical isolation/block of all pulmonary veins, as well as the “box”.
4. Acute procedural success of endocardial catheter procedure, defined as the percentage of subjects with successful electrical isolation/block of all pulmonary veins and the “box”, as well as bi-directional block of the cavo-tricuspid isthmus.
5. Freedom from Atrial Fibrillation, Atrial Tachycardia, Atrial Flutter without AAD, defined as no documented event >30 seconds in duration (or for the entire length of an ECG tracking) with no utilization of AADs beyond the blanking and AAD optimization periods, except as previously failed without an increase in dose. This endpoint will be measured through the 12-month, 2, 3, 4, and 5-year visits (Visits 11-15) via continuous 24- hour ECG monitor.
6. Freedom from Atrial Fibrillation, Atrial Tachycardia, Atrial Flutter regardless of AAD, defined as no documented event >30 seconds in duration (or for the entire length of a 30 second ECG tracing) regardless of AAD usage. This endpoint will be measured through the 12-month, 2, 3, 4, and 5-year visits (Visits 11-15 via continuous 24-hour ECG monitor).
7. Freedom from any documented AF, atrial flutter, or atrial tachycardia lasting >10 minutes in duration through the 12-month follow-up visit in the absence of Class I or III AADs (with the exception of previously failed AADs at doses not exceeding those previously failed).
8. Change in Quality of Life, defined as the total AFEQT score measured at the 12-month follow-up visit minus the score at the baseline visit. The score will be calculated per the AFEQT scoring manual.

2.1.4 Secondary Safety Endpoints

All secondary safety endpoints are supplemental and intended to provide a more complete picture of the overall safety profile for the DEEP procedure. They will not be tested for labeling purposes.

Statistical Analysis Plan		Page 9 of 22
Sponsor	Study	Version
AtriCure	DEEP Pivotal Study	Version 2.0

1. Major surgical events – This will be a composite safety endpoint within 30 days of the epicardial surgical procedure, as otherwise defined in the primary safety endpoint.
2. Major catheter events – This will be a composite safety endpoint within 7 days of the endocardial catheter procedure, as otherwise defined in the primary safety endpoint.
3. 30-day surgical SAEs – This will include all SAEs that occur within 30 days of the epicardial surgical procedure and that are adjudicated to be related to the device or to the procedure.
4. 12-month DEEP SAEs – This will include all SAEs through the 12-month follow-up visit that are adjudicated to be related to an AtriCure device or to either stage of the DEEP procedure.
5. Unresolved SAEs – This will include all SAEs through the 12-month follow-up visit that are adjudicated to be related to an AtriCure device or to either stage of the DEEP procedure and that are not fully resolved by the 12-months visit. These events shall include any procedure related deaths, strokes with residual disability, unresolved phrenic nerve damage, or other such events that are adjudicated to have resulted in chronic disability or permanent damage.
6. Any serious adverse event through the 12-month follow-up visit, regardless of attribution.
7. Incidence of stroke or TIA at 12-month, 24, 36, 48, 60-month visits.
8. Any esophageal injury that meets all of the following criteria: identified post epicardial ablation, adjudicated by core lab to be a thermal injury with perforation, and related to an AtriCure ablation device, through 30-days post epicardial procedure.

2.1.5 Secondary Health Economics Endpoints

All health economics endpoints are exploratory in nature.

1. Utilization of cardioversion, defined as the number of cardioversion events (visits) that a subject had in the past 12-month period. This endpoint will be measured at the 12-month, 2, 3, 4, and 5-year (Visits 11- 15) follow-up visits.
2. Hospital readmissions for AF, atrial flutter, or atrial tachycardia, defined as the number of readmissions in the past 12-month period. This endpoint will be measured at the 12-month, 2, 3, 4, and 5-year (Visits 11- 15) follow-up visits.
3. Total length of stay for all hospital readmissions for AF, atrial flutter, or atrial tachycardia, defined as the sum of the length of stay for each such visit within the last 12-month period. This endpoint will be measured at the 12-month, 2, 3, 4, and 5-year (Visits 11-15) follow-up visits.
4. Emergency Room Visits for AF, atrial flutter, or atrial tachycardia, defined as the number of visits in the past 12-month period. This endpoint will be measured at the 12-month, 2, 3, 4, and 5-year (Visits 11-15) follow-up visits.

Statistical Analysis Plan		Page 10 of 22
Sponsor	Study	Version
AtriCure	DEEP Pivotal Study	Version 2.0

3 Study Design

The study is a prospective, multicenter, single arm, pivotal study.

4 Sample Size Determination

The study is planned for up to 220 subjects and up to 35 sites (30 US and 5 OUS). Details regarding sample size determination are provided in the CSP.

5 Statistical Analyses

5.1 General Considerations

Except where otherwise specified, the following general principles apply to the planned statistical analyses. All statistical analysis will be conducted using SAS version 9.4 or later (SAS Institute Inc., Cary, NC) or other widely-accepted statistical or graphical software as required.

5.1.1 Descriptive Statistics

Continuous data will be summarized with mean, standard deviation, median, minimum, maximum, and number of evaluable observations. Categorical variables will be summarized with frequency counts and percentages. Confidence intervals may be presented, where appropriate, using the t-distribution for continuous data and Clopper-Pearson Exact method for categorical variables unless specified otherwise.

5.1.2 Study Day

Study day 0 is the date of the index procedure. Day in study will be calculated relative to the index procedure as follows:

$$\text{Study Day} = \text{Assessment Date} - \text{Index Procedure Date}$$

For each subject, duration in study will be based on last study contact date which is the latest date of all follow-up visits, assessments, adverse event onset or resolution, and study exit including date of death.

Duration variables will be calculated as follows:

$$\text{Duration Days} = \text{End Date} - \text{Index Procedure Date}$$

5.1.3 Visit Windows

Unless otherwise specified, visit based assessments will be analyzed for each analysis time point according to the nominal visit entered in the Case Report Form (CRF) regardless of if it is out of window.

Statistical Analysis Plan		Page 11 of 22
Sponsor	Study	Version
AtriCure	DEEP Pivotal Study	Version 2.0

5.2 Analysis Populations

Intent to treat patient population (ITT): The ITT subject population will include all subjects who have met all inclusion/exclusion criteria and on whom a procedure was attempted (defined as a subject who underwent induction of anesthesia).

Modified intent to treat patient population (mITT): The mITT subject population will include all subjects who attempted the Epicardial Procedure (defined as a subject who underwent induction of anesthesia) and have at least one post-procedure follow-up visit after the 2nd Blanking Period (with the 2nd blanking period defined as the 90-days post Endocardial Ablation Procedure) with non-missing primary effectiveness data.

Safety Population: The safety population will include all enrolled subjects that undergo induction of anesthesia.

Per protocol patient population (PP): The PP patient population will include all subjects who complete both the Epicardial Surgical Ablation Procedure and Endocardial EP Ablation Procedure.

AtriClip Effectiveness population: The AtriClip effectiveness population will include all ITT subjects for whom an attempt (entrance of the AtriClip into the chest wall) is made to place an AtriClip device.

The primary effectiveness analysis will utilize the mITT patient population as defined in this statistical analysis plan. The analysis will be repeated on the ITT and PP patient populations as supportive analyses. Secondary effectiveness analyses will be conducted on the mITT, the ITT and the PP patient populations. All safety analyses will utilize the safety population.

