The primary effectiveness and safety endpoints require similar numbers of patients, with the effectiveness endpoint driving the overall sample size. Due to the potential for significant loss to follow-up prior to the primary effectiveness endpoint at 12 months. In order to allow for an attrition rate of approximately 20%, this study will treat up to 220 subjects.

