9.5 Analysis Populations

The following analysis populations are defined for utilization in the data analysis:

- **Intent to treat patient population (ITT):** The ITT subject population will include all enrolled subjects who have met all inclusion/exclusion criteria.
- **Safety Population:** The safety population will include all enrolled subjects that undergo induction of anesthesia.
- **Per protocol patient population (PP):** The PP patient population will include all subjects who complete both the Epicardial Surgical Ablation Procedure and Endocardial EP Ablation Procedure.

- **AtriClip Effectiveness population:** The AtriClip effectiveness population will include all ITT subjects for whom an attempt (entrance of the AtriClip into the chest wall) is made to place an AtriClip device.

The primary effectiveness analysis will utilize the ITT patient population. Secondary effectiveness analyses will be conducted on the ITT and the PP patient populations. All safety analyses will utilize the safety population.

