2.1.1 Primary Effectiveness Endpoint

The primary effectiveness endpoint is freedom from any documented AF, atrial flutter, or atrial tachycardia lasting >30 seconds in duration through the 12-month follow-up visit in the absence of Class I or III AADs (with the exception of previously failed AADs at doses not exceeding those previously failed).

Any arrhythmia that occurs within the blanking period or the AAD Optimization period will not be considered a failure (Visit 5 up to Visit 10). The rhythm status used for evaluation of this endpoint will be derived from regularly scheduled monitoring (i.e. Holter, Zio™-Patch, or 30 second ECG) as well as any symptom driven monitoring that is performed.

The following scenarios shall constitute a failure of the primary effectiveness endpoint:

1. Any documented AF, atrial flutter, or atrial tachycardia lasting >30 seconds duration that occurs at any time beginning at the 6-month visit and through the 12-month visit. These will be

Statistical Analysis Plan		Page 6 of 22
Sponsor	Study	Version
AtriCure	DEEP Pivotal Study	Version 2.0

documented on any Core Lab – ECG form with a time interval of “6 Month Post Endocardial” or “12 Month Post Endocardial”.

2. Any previously failed class I or III AAD administered at a dose higher than baseline and between the 6-month visit date plus one day and the 12-month visit date.
3. Any newly introduced class I or III AAD usage beginning at the 6-month visit date plus one day and through the 12-month visit date.
4. DC cardioversion for AF, atrial flutter, or atrial tachycardia that takes place at any time beginning at the 6-month visit date and ending at the 12-month visit date.
5. Catheter ablation or surgical treatment for AF, atrial flutter, atrial tachycardia that takes place at any time beginning at the 3-month visit date and ending at the 12-month visit date.
6. Two or more repeat catheter ablations within the 2nd blanking period.
7. The use of a non-AtriCure study device for creation of any lesions during the surgical epicardial ablation procedure.

For the purposes of this study, atrioventricular nodal reentrant tachycardia (AVNRT), inappropriate sinus tachycardia, and Wolff–Parkinson–White syndrome (WPW) will not be considered procedure failures.

For this study, AtriCure defines failure of an antiarrhythmic drug (AAD) to include ineffectiveness or intolerance of the AAD.

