5.6.1.1 Primary Analysis

The statistical analysis of the primary effectiveness endpoint will consist of a comparison of the proportion of patients who remain a primary effectiveness success at the 12-month visit to a historical control rate that is based on results from the feasibility trials and published literature. The primary effectiveness endpoint will be assessed with the following hypothesis:

$$H_0: p_E \leq 0.60$$

$$H_a: p_E > 0.60$$

where p_E = the proportion of primary effectiveness success. The hypothesis will be evaluated using a one-sided chi-squared test at a one-sided $\alpha=0.025$ level of significance. The objective will be met if the estimated one-sided p-value is < 0.025. The mITT population will be the primary population for this analysis. Missing values will be treated as described in the Missing Values section 5.3 with the primary method being the LOCF method.

The proportion of primary effectiveness successes will be calculated with subjects as the experimental unit (i.e., the subject will be considered a success if no primary effectiveness failure was recorded from the 6-month visit through the 12-month visit). The numerator of the proportion will be the number of subjects who are a primary effectiveness success, and the denominator will be the total number of subjects. The endpoint will be presented with the numerator and denominator, the proportion and its 95% two-sided exact binomial confidence interval, and the one-sided p-value.

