5.6.1.2 Sensitivity Analysis

Sensitivity analyses for the primary effectiveness are discussed in the sections of this SAP related to missing data (different imputation schemes) and analysis populations (i.e., PP analysis).

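### The SAP's primary mITT set shuts out subjects who never have the endocardial stage, even when their outcome is known, whereas the supplied protocol keeps them in ITT and says how to score them

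*SAP*

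**What the plan says.** **Protocol (Rev H, 11May2021).** Section 9.5 states: "The primary effectiveness analysis will utilize the ITT patient population". Section 9.7.1 repeats this. Section 9.2.1 covers subjects who refuse the catheter stage or cannot have it. Their status is sought at 12 months after surgery, with the blanking and AAD-optimization periods counted from surgery. If status cannot be established, the endpoint is missing and goes to the missing-value methods, so the subject stays in the analysis. Sections 4.4 and 7.2 say that subjects converted to sternotomy or thoracotomy do not go on to the catheter stage but are followed for 12 months.

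**SAP (version 2.0).** Section 5.6.1.1 states: "The mITT population will be the primary population for this analysis". Sections 5.2 and 5.3 agree. Entry to mITT requires that the subject "have at least one post-procedure follow-up visit after the 2nd Blanking Period", with non-missing effectiveness data, and 5.2 defines that period as the 90 days after the endocardial procedure. ITT and PP are supportive repeats. Section 5.6.1.2 describes the population sensitivity work as "analysis populations (i.e., PP analysis"), and PP also requires both stages.

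**SAP scoring.** Under 5.6.1.1, "the subject will be considered a success if no primary effectiveness failure was recorded from the 6-month visit through the 12-month visit". Failure item 1 in 2.1.1 finds rhythm failures on any core-lab "ECG form with a time interval of “6 Month Post Endocardial” or “12 Month Post Endocardial". Item 7 is a failure on the day of surgery: "The use of a non-AtriCure study device for creation of any lesions during the surgical epicardial ablation procedure". The SAP does not repeat the protocol 9.2.1 rule.

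**The concern.** A subject with no endocardial procedure has no 2nd blanking period and so cannot have a visit after it. The deciding test therefore selects on something that happens after treatment starts, and partly on failure itself: an item 7 failure who never reaches stage 2 is dropped instead of counted.

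The trial has one arm and compares a proportion with a fixed 60%. No control group shares the selection, so removing subjects who did worse than the rest raises the tested rate directly. The ITT repeat could show how far the result depends on this. However, it does not decide success, and the SAP itself does not tell the analyst how to score these subjects there.

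**Working it through.** **Inputs.** From protocol 9.3 and 9.7.1: null rate 0.60, expected rate 0.70, one-sided alpha 0.025, N=182 for 80% power, and 220 treated ("In order to allow for an attrition rate of approximately 20%, this study will treat up to 220 subjects"). From protocol section 1.0: in the staged feasibility study 25 subjects had surgery and 24 had the endocardial procedure, so 1/25 = 4% did not (exact 95% CI 0.1 to 20%). Those stages were 1 to 10 days apart, against 91 to 121 days here, so 4% is only a starting point. The 10% share and every success rate among the excluded are assumptions.

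**The plan's own figure.** n = [(1.96·√(0.6·0.4) + 0.842·√(0.7·0.3)) / 0.10]² = 181.1, so 182. This matches without the continuity correction that the text mentions. Nothing below depends on that difference.

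**Reference case, all 220 analysed.** The smallest passing count is 147/220 (66.8%). Exact size at 60% is 2.2%, and power at 70% is 86%. The exact test (protocol) and the chi-squared test (SAP) give the same cut-offs at the sample sizes used here.

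**Effect of exclusion.** Let d be the share excluded and e their success rate, and hold the all-treated rate at 0.60. The rate in mITT is then p = (0.60 − d·e)/(1 − d), with n = 220(1 − d). The chance of passing is the exact binomial tail at the cut-off.

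| Success among excluded (e) | d = 4%: p (n=211, cut-off 141) | P(pass) | d = 10%: p (n=198, cut-off 133) | P(pass) |
|---|---|---|---|---|
| 90% | 0.5875 | 1.0% | 0.5667 | 0.2% |
| 60% | 0.6000 | 2.4% | 0.6000 | 2.2% |
| 50% | 0.6042 | 3.2% | 0.6111 | 4.6% |
| 30% | 0.6125 | 5.5% | 0.6333 | 15% |
| 0% | 0.6250 | 11% | 0.6667 | 47% |

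**One borderline result.** Take the smallest mITT pass with nine subjects excluded: 141/211 = 66.8%. If all nine failed, the all-treated result is 141/220 = 64.1%, exact one-sided p = 0.12. The same data pass on one set and miss on the other.

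**Power with all treated subjects kept.** Suppose 4% miss stage 2 and are observed, and the rest succeed at 70%. Then p = 0.96·0.70 + 0.04·e, which is 0.672, 0.684 or 0.696 for e = 0, 30 or 60%. Against 147/220, power is 58, 72 or 83%.

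**The case against.** - **The SAP may follow a later protocol.** SAP section 1 cites Revision H dated 28Sep2022, which was not supplied. A reader might infer that the SAP breaks with its governing protocol. The documents do not establish that; they show a conflict with the supplied version only. If the later version made mITT primary, the conflict goes, but the selection in the deciding test does not.
- **Assessing after stage 2 has a rationale.** Protocol Appendix 3 regards treatment as complete only after both procedures, and the 12-month window normally runs from the catheter procedure. This supports reporting mITT. It does not explain why subjects for whom 9.2.1 provides a scoring rule should leave the primary test.
- **The scoring rule can be borrowed.** SAP section 1 says to read it together with the clinical study plan. Protocol 9.2.1 can therefore govern the ITT repeat, and it would go too far to call scoring there undefined. It cannot bring anyone into mITT.
- **The ITT repeat need not default to success.** A reader might infer from item 1's post-endocardial labels that every subject without stage 2 would count as a success. That depends on case report forms not supplied. SAP 5.1.3 analyses by nominal visit, conversions are followed to a 12-month visit that may carry the label, and the drug, cardioversion, re-ablation and device items are not tied to those labels.
- **The bias can run either way.** A reader might infer that mITT must favour the device. It does so only if the excluded do worse than the rest. Protocol section 1.0 gives 35 to 90% success for minimally invasive thoracoscopic ablation, depending on lesion set and definition and not specific to conversions. The 47% needs both 10% excluded and no success among them. Item 7 failures succeed at 0% by definition, but the documents give no count of them or of conversions.

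**Conclusion.** The point stands as an inconsistency with the supplied protocol and as a selection built into the deciding test. As the SAP is written, subjects without stage 2 cannot enter, whether their outcome is observed, as with conversions and 9.2.1 subjects, or is already a failure under item 7.

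The size is conditional. If the excluded do worse than the rest, the 2.2% error rate rises: to 3 to 11% with 4% excluded and 5 to 47% with 10% excluded, as their success falls from 50% to 0%. If they do equally well nothing is lost, and if they do better the test is conservative. The documents do not show which case applies. A test that decides study success should not rest on that being favourable when the protocol already has a rule that keeps these subjects in. This should be settled before the analysis.

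**What to change.** 1. **Population.** In SAP 5.2, 5.3 and 5.6.1.1, make the SAP ITT set (eligible, anesthesia induced) primary and mITT supportive. Reconcile this with the protocol's ITT, which is all enrolled eligible subjects, and with treated subjects later found ineligible, whom the SAP ITT set drops and mITT keeps. If a later protocol changed the primary set, cite it and justify the choice.
2. **Scoring.** In SAP 2.1.1 and 5.3, write in the protocol 9.2.1 rule for subjects without stage 2. Let core-lab recordings timed from surgery count. Count item 7 as a failure whatever visits follow.
3. **Follow-up wording.** Protocol 4.4 lets a subject who withdraws before the endocardial stage exit after the 1-month visit, while 9.2.1 asks for 12-month status from one who refuses that stage. The two passages must be reconciled.
4. **Missing data.** Run the planned worst-case, best-case and break-even analyses on ITT. State how ITT subjects with no effectiveness testing are handled in the primary analysis, without dropping them or assuming success.

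**Cost.** Items 1, 2 and 4 need SAP wording and core-lab interval labels, and item 3 a clarification in the protocol. The reported success rate may be lower. With 220 treated, the pass mark becomes 147/220 in place of an mITT cut-off such as 141/211.

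Power is the real cost and should be restated. It is 86% if all are observed at 70% success, and 58, 72 or 83% if 4% miss stage 2 and succeed at 0, 30 or 60%. Counting 4% untested subjects as failures is the 0% case, 58%. That rule is therefore a trade-off, and collecting the 9.2.1 status is the way to limit it.
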